Protocol Number: 18-DA-N095

Title: **Just-In-Time Adaptive Interventions for Addictive Behaviors (JITAI)**

Date of this submission: December 18, 2019 / Version 2.2

NIH Principal Investigator:

[name].
Branch: CPTR
Institute: NIDA IRP
[name]
[name]
[name]
[contact]
email: [contact]

A. Précis

Background. Our research group has made extensive use of ecological momentary assessment (EMA) to understand people's daily experiences with opioid craving, use, and lapse. We have also administered clinic-based psychotherapies such as cognitive-behavioral therapy (CBT), in which clients learn to avoid, escape, resolve, or reframe problems (such as stress) that can trigger lapses to drug use. CBT contrasts with ACT (Acceptance and Commitment Therapy), a mindfulness-based approach in which difficult thoughts and feelings are viewed as necessary and potentially valuable components of a full life, to be experienced observantly rather than resolved or reframed. CBT and ACT can and do coexist in a single treatment plan, but we know of no systematic attempt to reconcile their differences. We have also not tried to administer either of them on a mobile device.

Objective. To test a just-in-time adaptive intervention (JITAI)—a treatment given when and where it is needed. Our JITAI will be delivered via smartphone app and will combine elements of two widely used treatments for addiction: CBT and ACT. Our goal is *not* to bring another branded app onto the market, but rather to clarify when and for whom the generic components of such apps are effective or not. This will include determining when CBT is more helpful than ACT and vice versa.

Participant population. Outpatient adults who are in treatment for opioid use disorder (OUD)—up to 185 enrolled (35 for a formative-interview phase, 150 for a trial) for a target of 115 evaluable (30 interviewees, 85 trial participants). Target enrollment will include 40% women and 60% minorities (mostly African-American). In the trial, some participants will receive buprenorphine in our clinic, and others will be receiving buprenorphine or methadone elsewhere; this is a procedural matter, not a component of the experimental design.

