Primary outcome measures: (1) Proximal effects of CBT and ACT messages in the JITAI group: decreases over 20-minute intervals in craving and negative mood, with increases in self-efficacy; (2) strategy-situation fit in the JITAI group; (3) group differences in distal effects of treatment (week 11 versus week 2) in terms of self-efficacy and coping flexibility.

Secondary outcome measures: (1) Trait predictors of differential responses to CBT and ACT, in the JITAI group; (2) group differences in frequency of opioid-positive urine over time; (3) time courses of responsiveness to ACT vs. CBT, in the JITAI group; (4) whether the intervention types that benefit participants most when “pushed” by the app are the same ones participants choose when subsequently given the opportunity to “pull” interventions.

B. Table of Contents

A. Précis.....	2
B. Table of Contents.....	4
C. Background.....	5
1. From mobile assessment to mobile treatment: a microrandomization approach	5
2. Momentary interventions to be tested in the first arm of this protocol.....	7
3. Two ways to deliver a momentary intervention: push versus pull.....	9
4. Rationale for a multiple-arm protocol.....	10
D. Study objectives	10
E. Study design and methods	11
1. Overview of arm 1.....	11
2. Arm 1, Phase 1: Formative interviews.....	12
3. Arm 1, Phase 2: Clinical trial with microrandomization.....	12
F. Inclusion and exclusion criteria	24
1. Inclusion criteria.....	24
2. Exclusion criteria.....	24
G. Clinical and laboratory methods	25
H. Collection and storage of human specimens or data.....	30
I. Statistical analysis.....	31
1. Outcome measures.....	31
2. Analysis of study outcomes	31
3. Criteria for statistical significance.....	34
J. Required sample size	35
K. Plans for enrollment at multiple sites.....	36
L. Human-subjects protection plan	36
1. Rationale for subject selection based on gender/ethnic/race categories at risk.....	37
2. Recruitment plan	37
3. Justification for exclusion of vulnerable populations	38
4. Evaluation of risks/discomforts and benefits ratio	39
5. Subject monitoring	43
6. Conflicts of interest.....	44
M. Protection of participants' privacy and confidentiality	45
N. Study agents/interventions.....	45
O. Plan for reporting unanticipated problems and adverse events.....	45
P. Data and safety monitoring	45
Q. Clinical monitoring plan.....	46
R. Data/records management	46
1. Quality assurance.....	46
2. Relationship to other protocols	47
3. Data-sharing description.....	47

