2. *Strategy-situation fit.* The effects of the messages will be moderated by the circumstances in which they are provided (Haines et al., 2016). For example:

- In situations that are under the participant's control, greater proximal benefits will be associated with active CBT strategies such as avoidance or direct action.
- In situations that are largely out of the participant's control, greater proximal benefits will be associated with acceptance (ACT). Some CBT strategies, such as distraction or cognitive reappraisal of the situation (i.e., interpreting a seemingly negative event as a positive event) might also be useful in those situations, but there is evidence that accepting one's own negative thoughts and emotions (an ACT strategy) confers unique benefits beyond those of reappraisal, shortening the duration of negative mental experiences (Ford et al., 2017).

Hypotheses for *distal* effects of intervention (time scale of weeks):

3. *Main effect of intervention.* The group randomized to JITAI will have better outcomes (e.g. less drug use, higher self-efficacy, a greater increase in flexibility of coping styles) than the EMA-only control group when assessed at week 11.
4. *Differential responses over time.* This “distal” effect is really a summary of proximal effects. We and others have found that drug abstinence is delayed after initiation of CBT, as skills become practiced and integrated into daily life (Carroll et al., 1994; Epstein et al., 2003). We hypothesize, however, that CBT messages will be rated as helpful almost immediately, due to their pragmatic, straightforward nature. ACT messages, which are usually more oblique and koanlike, may have to be seen several times, or lived with for several weeks, before being rated as helpful—but may also stand up better to repetition.
5. *Trait predictors of responsiveness.* Like responsiveness over time, this “distal” effect is really a summary of proximal effects. Although we are not powering the study to assess treatment matching at the person level, we will examine whether trait variables such as personality and preferred coping styles are associated with differential responsiveness to CBT-based versus ACT-based messages.

Push versus pull:

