2. Analysis of study outcomes

Hypothesis 1, proximal: Main effect of messaging (delivery of either a CBT-based or ACT-based message will increase self-efficacy and decrease cravings and other negative states 20 minutes later, compared with the control message).

We will use multilevel random-intercept models (with data from the JITAI group only) to test the hypothesis of a proximal benefit of messages. The dependent variables, in separate models, will be participants' ratings of self-efficacy, craving, mood, and message helpfulness in EMA "post" assessments, controlling for the ratings in "pre" assessments. The main independent variable will be message type: active (CBT or ACT) versus none ("thank you" control condition). We will use an autoregressive error structure to account for within-person correlations. A significant beneficial effect on any of the outcome measures (self-efficacy, craving, mood, message helpfulness) will be taken as partial support for the hypothesis; significant beneficial effects on all the outcome measures will be taken as full support.

Hypothesis 2, proximal: Strategy-situation fit (the effects of the messages will be moderated by the circumstances in which they are provided).

The main analysis here (again, with data from the JITAI group only) will be a test of whether CBT messages are most effective in controllable situations and ACT messages are most effective in noncontrollable situations. We will categorize a situation as *noncontrollable* when a participant gives a response of less than 50/100 on either of these two "pre" items: (1) "I could easily be somewhere else right now if I wanted," (2) "I could easily get out of what I'm doing right now." Otherwise, we will categorize the situation as *controllable*. In the subset of instances in which an active message was given, multilevel models similar to those for hypothesis 1 will be run with the predictors Intervention Type (either CBT or ACT), controllability (y/n), and their interaction. A significant interaction (in the expected direction) on any of the outcome measures (self-efficacy, craving, mood, message helpfulness) will be taken as partial support for the hypothesis; significant beneficial effects on all the outcome measures will be taken as full support.

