Hypothesis 4, distal: Differential responses over time (CBT messages will be rated as helpful almost immediately; ACT messages may have to be lived with for several weeks, but may also stand up better to repetition).

In the JITAI participants, we will test this hypothesis with time-varying effect models (TVEMs) (Shiyko et al., 2012). These are extensions of multilevel models that can assess whether the relationship between a predictor and outcome becomes larger or smaller over time. If we see the predicted patterns of change on the “post” item “How useful was the message?,”

we will take that as full support for this hypothesis. If we see it only on other outcome measures (self-efficacy, craving, mood), we will take that as partial support.

Hypothesis 5, distal: Trait predictors of responsiveness (although we are not powering the study to assess treatment matching at the person level, we will examine whether trait variables such as personality and preferred coping styles are associated with differential responsiveness to CBT-based versus ACT-based messages).

This will be tested (with data from the JITAI group only) in multilevel models similar to those for hypothesis 1, with the predictors Intervention Type (either CBT or ACT), Trait, and their interaction. Specific predictions to be tested are: (1) high scorers on the baseline “Need for Closure” scale will benefit more from CBT messages than from ACT messages; (2) participants with steep discounting functions on the Monetary-Choice Questionnaire will be initially resistant to ACT.

The NEO personality inventory and our other trait measures offer many potential predictors, and we do not have *a priori* hypothesis for most of them. In reporting results from any of these analysis, we will specify that they were exploratory, and we will state clearly how many analyses we ran.

Hypothesis/analysis 6 (push versus pull: we will also assess, but have no directional predictions about, whether the intervention types that seem to benefit participants most when “pushed” by the app are the same ones that participants choose when subsequently given the opportunity to “pull” interventions).

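### The planned trait model (Hypothesis 5) has no control reference, so for craving, mood and self-efficacy it cannot separate message benefit from trait-related natural change

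*Combined protocol and SAP*

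**What the plan says.** The Objective in the Précis is to "clarify when and for whom the generic components of such apps are effective or not"; finding out when one approach is more helpful than the other is named as part of that goal. The first secondary outcome is narrower: "Trait predictors of differential responses to CBT and ACT, in the JITAI group". Section D, Hypothesis 5, likewise asks whether traits are "associated with differential responsiveness to CBT-based versus ACT-based messages".

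Section I.2 gives the Hypothesis 5 analysis. It is to be tested, in the JITAI group only, "in multilevel models similar to those for hypothesis 1", and "with the predictors Intervention Type (either CBT or ACT), Trait, and their interaction". Two specific predictions follow. High Need for Closure scorers should gain more from CBT than from ACT, and steep discounters on the Monetary-Choice Questionnaire "will be initially resistant to ACT".

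The neighbouring analyses do not cross a trait with message versus control. Hypothesis 1 does use the control moments ("The main independent variable will be message type: active (CBT or ACT) versus none") but has no trait term. Hypothesis 2 concerns situations and states its restriction outright: "In the subset of instances in which an active message was given". Hypothesis 3 compares the randomized groups, Hypothesis 4 concerns change over time, and Hypothesis 6 estimates person-specific CBT-versus-ACT slopes. Section E.3 also promises checks on Twelve-Step involvement and on previously interviewed participants, but gives no model for either.

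Section E.3, on the post assessment, assigns the control condition the job of showing what 20 minutes do on their own. It also limits the usefulness rating to moments when a CBT or ACT message was given.

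**The concern.** A statement that a message works for some people and not for others, or that some people resist ACT, compares a message with no message. The Hypothesis 5 predictor has only the values CBT and ACT. A thank-you moment has no value on it, so the natural reading is that these moments drop out. The trait slope then has no reference for what would have happened over 20 minutes without a message.

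Adjusting for the pre rating does not supply that reference. A single 0-100 rating is an imperfect measure of a person's usual level, so a trait related to that level can still predict the post rating when no message was shown.

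At stake is how two secondary findings are worded. Steep discounters could be reported as resistant to ACT when ACT helps them as much as anyone. People for whom neither message works could not be told apart from people whose craving or mood simply drifts differently.

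**Working it through.** **The plan's own figure.** Section J gives no figure for Hypothesis 5. Its nearest figure is 25 evaluable JITAI participants for Hypothesis 1: active versus control, power 0.90, mean d = 0.15, 56 days, 4 decision points a day, randomization probability 0.67, mean availability 0.60. A micro-randomized-trial calculation used a noncentral F with 3 and N − 6 degrees of freedom and noncentrality N × β′[Σ τ_t ρ(1 − ρ) Z_t Z_t′]β. It returned 25 to 27 across several shapes for the effect and availability curves. The calculator's defaults are not in the protocol, so quadratic forms with three parameters were assumed. The plan's inputs are therefore usable below.

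**What the model can identify.** Score each outcome so that higher is better, in residual SD units per SD of trait. Let
- n = trait slope of natural 20-minute change (control moments),
- b_C = trait slope of CBT benefit over control,
- b_A = trait slope of ACT benefit over control.

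Active moments alone give two slopes for three unknowns:
- slope at CBT moments = n + b_C
- slope at ACT moments = n + b_A
- interaction = (n + b_C) − (n + b_A) = b_C − b_A

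The difference b_C − b_A is identified; b_A and b_C separately are not. Control moments add a third slope, n, and then all three are identified.

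| Scenario | b_C | b_A | n | CBT slope | ACT slope | trait × (CBT − ACT) | trait × (ACT − control) |
|---|---|---|---|---|---|---|---|
| A: trait lowers ACT benefit | 0 | −0.15 | 0 | 0 | −0.15 | +0.15 | −0.15 |
| B: trait raises CBT benefit, worse natural change | +0.15 | 0 | −0.15 | 0 | −0.15 | +0.15 | 0 |
| C: trait lowers both benefits | −0.15 | −0.15 | 0 | −0.15 | −0.15 | 0 | −0.15 |
| D: worse natural change only | 0 | 0 | −0.15 | −0.15 | −0.15 | 0 | 0 |

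A and B agree on everything the active-only model estimates, and so do C and D. Only the last column, which needs control moments, separates them. A simulation (50 participants, 45 moments per condition, 2,000 runs) reproduced these entries to within 0.001. The size 0.15 is illustrative.

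**Precision of the added contrast.** Inputs are from Section J; an equal CBT/ACT split is assumed.
- Available moments per person: 56 × 4 × 0.60 = 134.4
- Per condition: m = 134.4 / 3 = 44.8
- SE of a trait slope, ACT − control or CBT − ACT: √[(2/m + τ²)/N], with N = 50 and τ the SD of person-specific effects (assumed)
- τ = 0: √[(2/44.8)/50] = √(0.0446/50) = 0.030
- Slope detectable with 80% power, two-sided 0.05: (1.960 + 0.842) × SE = 0.084 at τ = 0, 0.103 at τ = 0.15 and 0.145 at τ = 0.30
- Pooled active − control replaces 2/m by 1.5/m: 0.072, 0.094 and 0.139

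With equal allocation, ACT − control and CBT − ACT share one formula and so have the same precision. Using only the 49 pure-push days gives 49 × 4 × 0.60 / 3 = 39.2 moments per condition, which affects both alike.

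**The case against.** The strongest reply is that the analysis matches its hypothesis. The secondary outcome and Hypothesis 5 are both worded as CBT versus ACT, and the specific aims in Section D do not promise a test of who benefits compared with no message. This stands. The mismatch is only with the broader Précis goal and with the discounting prediction, which is about ACT alone. The Need for Closure prediction is relative and the model answers it; there is no need to require that CBT also beat control.

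Stronger readings are tempting and are not supported:
- **That Hypothesis 5 states that control moments are discarded.** Only Hypothesis 2 says so. For Hypothesis 5 it follows from the two-level predictor, and the reference to models like those of Hypothesis 1 leaves some ambiguity.
- **That the interaction alone misleads.** The model also has a Trait term. If natural change is unrelated to the trait (n = 0), a trait that only raises CBT benefit shows a zero slope at ACT moments, and a trait that lowers both benefits shows up as a Trait effect. The difficulty arises because n is unknown without control moments.
- **That resistance to ACT cannot be examined at all.** Low usefulness ratings of ACT messages among steep discounters are one reading of resistance and need no control. They show how messages were received, not change in craving, mood or self-efficacy.
- **That the omitted contrast is markedly more informative.** Information per push is (2/3)(1/3) = 0.222 for pooled active versus control, against (2/3)(1/4) = 0.167 for CBT versus ACT, a ratio of 1.33. That ratio does not apply to ACT versus control. For trait slopes even the pooled gain shrinks, to 0.139 against 0.145 at τ = 0.30.

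It is also fair to say that Hypothesis 5 is openly unpowered and mostly exploratory. That limits severity. But it concerns precision, whereas this gap would remain with any number of participants, and discounting is one of the two named predictions.

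**Conclusion.** The point holds in limited form. On craving, mood and self-efficacy, no analysis with a stated model separates a trait's effect on message benefit from trait-related natural change. The trial therefore cannot say on these outcomes for whom messages are effective, or whether steep discounters resist ACT. The discounting prediction has a second gap: it concerns the early period, and the Hypothesis 5 model has no time term.

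The conclusion rests on reading the two-level predictor as excluding control moments, and on natural change possibly varying with the trait. The documents give no figure for the latter, so the size of any misreading is unknown. Severity is minor to moderate: no primary conclusion, randomization or data collection is affected.

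**What to change.** In Section I.2, Hypothesis 5:
1. For craving, mood and self-efficacy, fit the model on all push moments with a three-level message factor (control, CBT, ACT) × trait. State that control moments are included.
2. Report trait × (active − control) and trait × (ACT − control) beside trait × (CBT − ACT).
3. For the discounting prediction, add message × trait × time and define the early period in advance. Describe steep discounters as resistant to ACT on these outcomes only if the early trait × (ACT − control) contrast shows a smaller ACT benefit.
4. Keep the Need for Closure prediction, and the usefulness rating for all traits, as CBT versus ACT.

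If the sponsor prefers the present model, the alternative is to narrow the Précis goal to relative response and reword the discounting prediction to match.

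The cost is plan wording and a few more contrasts per trait and outcome, to be included in the count of analyses that the plan already promises to report. No extra participants or assessments are needed. The early-period contrast uses fewer moments, so its detectable slope will be larger than the full-period figures above.
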